### ***The Emotional Stroop task***

For the emotional Stroop task (EST), three word lists are prepared, a threat list, a negative list, and a neutral list. Each list contains 30 monosyllabic words. The threat words include things encountered in dangerous situation (e.g. gun), the negative words are negative in valence, but not related to threat (e.g., bad). The neutral words are not threatening nor negative (e.g., tune). The three words lists are equated across lexical features including: length, frequency, orthographic, and phonological neighborhood size. Using the ELP database, the words are also equated on average naming latency, naming accuracy, lexical decision time, and lexical decision accuracy (Balota et al., 2007). The task contains 9 experimental blocks, each consisting of 30 color word naming trials from one of our EST lists. The order of the words within each list is randomized across presentation blocks. Within each trial, participants first view a fixation cross for 1 second, which is replaced by a list item that remains on the screen for 2 seconds. An experimenter codes the participants response as correct (i.e., correct color identification), incorrect (i.e., did not name a color, named the wrong color, or named the word), or as a noise trial (e.g., the participant coughs, etc.). The items are centered horizontally/vertically on a 43.5 by 35cm screen and positioned at eye-level approximately 110cm from the head. Items are presented in red, blue, or green font, and item color is randomly assigned. Reaction times are measured using a dual-plane accelerometer attached to the lower lip and digitized at 1kHz using a Grass amplifier. Voice onset is determined by a sharp increase in the amplitude of the accelerometer signal, which produces response time accuracy near 1ms.

In addition to the emotional Stroop task, subjects will also view simple images (no more disturbing or violent than subjects can be exposed to in their everyday life) and respond to the images by pressing button. Movements in the MEG scanner will be also measured.

### **Buccal Cheek Brush for genetic sampling:**

During the initial research assessment session, the buccal cheek brush will be performed

collecting DNA samples for genotyping of the OTR. Cheek cells will be collected using a commercially-available kit (Qiagen) and will require participants to gently brush the buccal cavity 10-20 times with the pliable brush. DNA will be extracted and amplified via conventional PCR. Participants will be genotyped for a minimum of 11 single nucleotide polymorphisms (SNPs) in *OXTR* that have been implicated in social and psychiatric disorders (Aspé Sánchez et al., 2015), as well as several polymorphisms in *CD38*, a gene that codes for a glycoprotein that regulates oxytocin signaling and social function (Feldman et al., 2012). PCR products with blinded codes will be sequenced at the UNMC Sequencing Core Facilities.

Collection of the genetic sample is OPTIONAL and not mandatory for study participation.

### **Oxytocin/placebo administration**

If the participants are assigned to the oxytocin treatment arm by randomization, they will be initiated on oxytocin administration after the MRI visit 1 and MEG visit 1. Following previous studies using intranasal oxytocin administration (Dadds et al., 2014; Guastella & MacLeod, 2012; MacDonald et al., 2011), subjects weighing >40kg will receive a total of 24 IU of oxytocin delivered as 2-6 IU puffs to each nostril once daily. Subjects weighing <40kg will receive a total of 12 IU of oxytocin delivered as 1-6 IU puff to each nostril daily. Participants will receive 14 to 21 days of daily oxytocin/placebo administration. After 14 days of oxytocin/placebo administration, participants will be scheduled to have MRI visit 2 and MEG visit 2. After those two visits are completed, participants will stop oxytocin/placebo administration. Participants who are assigned to placebo treatment branch will receive identical bottles and instructions for delivery of all the other ingredients of nasal spray except oxytocin. The instruction and demonstration will be given to the parents or parent/legal guardian as the first administration of the nasal spray done at the clinic by either child and adolescent psychiatrist or advanced practice registered nurse. The daily administration will be done by dispatching either oxytocin or placebo nasal spray to the parents of the participants. The oxytocin and placebo nasal spray will be prepared by the University of Nebraska Medical Center research pharmacist who will be un-blinded to each subject's treatment assignment. The randomization will be done by the department of pharmacology by a computer-programmed randomization procedure.

The participants will have one or two weekly visits to the clinic, depending on the duration of the trial (one if it is 14 days, 2 if it is more than 14 days and less than 21 days). If the participant is having two weekly visits, the first will be conducted by phone. They will be assessed for symptom level, nasal spray tolerance, and assessment of adverse effects. Participants will be initiated on psychiatric treatment if it is indicated by change of their psychiatric condition (such as worsening of psychiatric symptoms). In this case, they will be

withdrawn from the study.

The second fMRI and MEG scans will be completed after 14-21 days of oxytocin/placebo treatment. The final research assessment will be completed at that time. The duration of oxytocin treatment (14 to 21 days) will be decided by the scheduling and completion of MRI visit 2 and MEG visit 2.

Compliance with medication and adverse effects will be assessed at each visit. If during the course of the study it is discovered that the participant has a disorder or condition that would disqualify him/her (e.g., unexpected side effect of oxytocin that will necessitate cessation of the treatment or medical compromise that will make it impossible to continue oxytocin treatment), but needs further evaluation, the participant will be immediately referred for further clinical assessment and intervention to their primary care provider or, if requested, an appropriate department at the University of Nebraska Medical Center.

**C. Identify all procedures, interventions, evaluations and tests that are**

**1) Performed solely for research purposes.**

1. WASI-II for IQ measurement
2. Diagnostic and symptom profile measurements (KSADS-PL, ARI, ICU, BASC-3, RPAQ)
3. fMRI and MEG scans
4. Buccal musoca sampling for oxytocin receptor analysis
5. Oxytocin or placebo treatment
6. Assessments of medication compliance and adverse effects
7. Urine drug screen
8. Urine pregnancy testing
9. CGI-Severity and CGI-Improvement ratings (CGI-S and CGI-I)
10. Children's Global Assessment Scale (CGAS)

**2) Performed more frequently than they would be if the subject was not participating in the research.**

Urine drug screen and pregnancy test may not be done in regular outpatient care. Neuroimaging may or may not be done as part of clinical practice. Assessment of symptoms and treatment compliance and related effects are standard practice.

**3) Performed on the subjects in the course of their normal clinical care (i.e. for diagnostic or treatment purposes) where the data are used for research.**

Clinical assessment for psychiatric symptoms.

**D. Does this research involve genetic testing?**

Yes

**1) Is the genetic testing a portion of a more comprehensive therapeutic or non-therapeutic study?**

Yes

**a) Is the genetic testing portion of this research directly relevant to the subject's disease or condition?**

Yes.

**2) Will identifiers (e.g., name, initials, patient identification number, or code) be maintained which allow anyone to link the results of the genetic tests either directly or indirectly to the subject or will potentially identifying information be obtained from, or about, family members?**

Yes

**E. Will any un-used human biological material (HBM) be used to create a tissue bank for future research?**

No

**F. Describe briefly the statistical methods used to analyze the data.  
Analysis of data/study outcomes**

The purpose of the current study is to determine the impact, as indexed by Blood Oxygen Level Dependent (BOLD) response as well as improvement in symptom profiles, of the administration of oxytocin on pathophysiology of irritability and emotional dysregulation across various diagnoses of disruptive behavior and mood disorders. Using the two biomarker tasks, fear expression processing and affective Stroop, we will be able to determine the extent to which administration of oxytocin reduces the increased BOLD responses in neural areas (i.e., amygdala) to negative emotional stimuli. We will also determine the improvement of symptom profiles by evaluations including ARI, BASC-2, ICU and RPAQ.

The relationship between symptom measurement and neural response changes will be analyzed using both regression and categorical modes. *Hypothesis A, that oxytocin will improve irritability and emotional dysregulation, as well as reduce BOLD responses in amygdala to negative emotional stimuli, compared to placebo* will be tested by (1) a two sample t-test between placebo and oxytocin-treated groups on the symptom profile changes of the ARI, BASC-2, ICU, RPAQ; CGI-S and CGI-I; (2) a two sample t-test between placebo

and oxytocin-treated groups on the change of BOLD responses; (3) ANCOVAs with the treatment groups and the change of symptom profiles as the covariates on the change of BOLD responses.

To account for potential non-linear relationships polynomial fits will be explored, and categorical comparisons will also be made, of responders versus non-responders (with responders defined as those with 0.4 standard deviation of positive change on the symptom measurement scales, including the ARI, CBCL, ICU, and RPAQ).

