## **CHARACTERISTICS OF THE SUBJECT POPULATION**

### **4. Accrual**

**Is this study conducted solely at sites under the oversight of the Joint Pediatric IRB (e.g. UNMC, TNMC, CH&MC, UNO)?**

Yes

**A. What is the total number of subjects (per group, as applicable) needed to complete the research in order to achieve the scientific objectives of the research?**

104 subjects are needed to complete the trial (52 per treatment group).

**B. What is the statistical or other justification for the total number of subjects needed to complete the research in order to achieve the scientific objectives of the research?**

The primary outcome is the change of Affective Reactivity Index (ARI) from the baseline to the last visit. A sample size of n=52 per group will provide 80% power to detect a difference between the group means of -4.0 in the change of ARI of -4.0 at the significance level of

0.05 using a two-sided two-sample t-test, assuming the mean of -4.0 and the standard deviation of 7.2 in the oxytocin group, and the mean of 0 and the standard deviation of 7.2 in the placebo group.

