**9. Inclusion Criteria**

**What are the specific inclusion criteria?**

**Children/adolescents with disruptive behavior and mood disorders (ADHD, ODD, CD, DMDD)**

1. 10-18 years of age
2. A current diagnosis of ADHD, ODD, CD, or DMDD as determined by the Kiddie-SADS, lifetime version
3. Clinically significant level of irritability as defined by a score of  $\geq 4$  on the Affective Reactivity Index (ARI) (Stringaris et al., 2012)
4. If currently on medication, medication treatment must be stable for at least 6 weeks

with a stimulant medication, alpha 2 agonist, atomoxetine, antipsychotics, mood stabilizers or antidepressant.

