**Symptom Profile Assessment:**

The Affective Reactivity Index (ARI) will be completed at the initial research assessment session and the final research assessment session. ARI is a 7 item inventory (self-report

and parent-report versions) specifically designed to measure irritability and emotional dysregulation (Stringaris et al., 2012). This will be used to measure the outcome of improvement in irritability by oxytocin treatment.

The Behavior Assessment System for Children, second version (BASC-3) will be completed at the initial research assessment session and the final research assessment session. BASC-3 is parent-reported, well-established scale for externalizing/internalizing problem of children and adolescents (Reynolds, 2015). This will be used to measure the outcome of improvement in emotional dysregulation and other related symptoms (externalizing behavior) by oxytocin treatment.

The Inventory of Callous Unemotional trait (ICU) will be completed at the initial research assessment session and the final research assessment session. ICU is a 24 item inventory specifically designed to measure callous-unemotional trait in children and adolescents (Berg et al., 2013; Frick, 2004). This will be used to measure outcome of improvement in callous-unemotional trait by oxytocin treatment. This will be also used to assess covariate function of callous-unemotional trait on treatment response.

The Reactive-Proactive Aggression Questionnaire (RPAQ) will be completed at the initial research assessment session and the final research assessment session. RPAQ is a 23 item inventory (self-report) specifically designed to measure two different types of aggressive behavior, i.e., reactive and proactive aggression (Raine et al., 2006). This will be used to measure outcome of improvement in related symptom of aggressive behavior by oxytocin treatment.

The Clinical Global Impression: Severity and Clinical Global Impression: Improvement scales (CGI-S and CGI-I) will be used at study entry and study completion to quantify, based on clinician's global assessment of the individual, the severity of symptoms compared (study entry and completion) and the degree of improvement (study completion) which may or not be attributable to the study intervention. Other symptom profile measurements will be used to assist the clinician in the rating of this measure.

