### **Statistical methods for the internal pilot study**

The first 20 patients will be enrolled and randomly assigned into placebo and oxytocin group. The primary outcome ARI will be measured at the baseline and last visit for each patient. The change of ARI will be calculated as the measure at the last visit minus the measure at the baseline for each patient. The treatment status of each patient will be labeled as A and B by the third party, and all persons associated with the internal pilot study will be kept blinded for group assignment. The SD of the change of ARI will be estimated for each intervention group, and will be used to compute the pooled SD for the internal pilot study. Recalculation of the sample size will be performed using a two sample independent t-test and the pooled SD. The retention rate will be assessed as well.

The data on genetic polymorphisms and OT-treatment outcomes on the neural and psychological measures will be used primarily as pilot data to advise future larger-scale studies. OXTR SNPs vary in frequency in western populations, but there should be sufficient exemplars of varying genotypes to allow preliminary analyses. For example, a commonly-identified OXTR SNP associated with variation in social behavior (rs53576) occurs in frequencies of 53.5% and 46.5% for the risky genotype (A/A and A/G) relative to resilient genotype (G/G) in a Caucasian sample (Jacob et al., 2007).

Finally, we will simultaneously test all measures (e.g., at baseline) in a multivariate analysis to determine the most important measures for predicting outcome in terms of behavioral change (Ecker et al., 2010). It is hoped that this will show which ones of the variables are the best predictors of treatment response, and which aspects are best influenced by treatment.

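### The primary ARI comparison is an unadjusted t-test on change; adding baseline ARI, already collected for every child, costs at most about 0.4 points of power and may gain precision

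*Combined protocol and SAP*

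**What the plan says.** All references are to the combined protocol and SAP.

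- **Primary outcome and sample size (section 4.B).** "The primary outcome is the change of Affective Reactivity Index (ARI) from the baseline to the last visit". The size of 52 per group is derived at the 0.05 level "using a two-sided two-sample t-test, assuming the mean of -4.0 and the standard deviation of 7.2 in the oxytocin group", with a mean of 0 and the same SD in the placebo group.
- **Analysis (section 12.F, Hypothesis A).** Test (1) is a "two sample t-test between placebo and oxytocin-treated groups on the symptom profile changes of the ARI" and the other symptom scales. No covariate is named.
- **Internal pilot (section 12.F).** "Recalculation of the sample size will be performed using a two sample independent t-test and the pooled SD".
- **Baseline data.** Section 9, item 3 requires a "Clinically significant level of irritability as defined by a score of" 4 or more on the ARI. Section 12.B states: "The Affective Reactivity Index (ARI) will be completed at the initial research assessment session and the final research assessment session".
- **The only ANCOVA (section 12.F, test 3).** This is "ANCOVAs with the treatment groups and the change of symptom profiles as the covariates on the change of BOLD responses". Its outcome is imaging change, and its covariate is symptom change rather than baseline ARI.

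**The concern.** A change score is the final value minus 1 times the baseline value. If final ARI rises by less than one point per point of baseline, which is the usual pattern of regression to the mean, subtracting the whole baseline over-corrects. Two things follow. The change score carries variation that the baseline could have explained, so the interval for the treatment effect is wider than it need be. And if one arm happens to start higher, that arm appears to improve more for reasons unrelated to treatment. The t-test is unbiased over repeated randomisations; the shift exists only given the imbalance actually observed.

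The planned design has about 80% power with nothing in reserve, and section 12.B describes computer-programmed randomisation without mentioning stratification by baseline ARI. Adjustment would address both consequences with data already collected.

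**Working it through.** **Inputs from the plan (section 4.B).** Difference 4.0; SD of change 7.2 in each arm; two-sided 5%; 52 per arm.

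**Assumed inputs, not in the documents.** ρ is the correlation between baseline and final ARI, taken from 0.3 to 0.9. k is baseline SD divided by final SD, taken as 1.0, 0.8 or 0.7. The change SD is held at 7.2 throughout.

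**Step 1: the plan's own figure.** The standard error is 7.2 × √(2/52) = 1.412. The exact (noncentral t) power with 102 df is 80.1% at 52 per arm and 79.3% at 51, so the stated 52 reproduces. The 95% half-width is 1.9835 × 1.412 = 2.80.

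**Step 2: variance with adjustment.** Before the covariate's own cost,

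Var(adjusted) / Var(change) = (1 − ρ²) / (1 + k² − 2ρk).

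At k = 1 this is (1 + ρ)/2. It equals 1 only when ρ = k, that is, when the slope of final on baseline (ρ/k) is 1. In general it is 1 − r², where r is the correlation of baseline with change, so it cannot exceed 1.

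**Step 3: cost of the covariate.** The degrees of freedom fall from 102 to 101 and the critical value moves from 1.9835 to 1.9837. The average variance inflation is 1 + 1/(104 − 4) = 1.01. With a ratio of 1, power is 79.7%, a loss of 80.1 − 79.7 = 0.4 points. There is a net gain in variance once r² exceeds 1 − 1/1.01 = 0.0099, that is, once |r| is above about 0.1.

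**Step 4: effect of a chance imbalance.** For a baseline difference of one standard error, the unadjusted estimate shifts by (ρ/k − 1) × SD_base × √(2/52), with SD_base = 7.2k / √(1 + k² − 2ρk). Example at k = 1, ρ = 0.5: SD_base = 7.2, and the shift is −0.5 × 1.412 = −0.71 points.

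| k | ρ | Variance ratio | Adjusted power | Half-width | Shift, absolute (ARI points) |
|---|---|---|---|---|---|
| 1.0 | 0.3 | 0.650 | 93.4% | 2.27 | 0.84 |
| 1.0 | 0.5 | 0.750 | 89.7% | 2.44 | 0.71 |
| 1.0 | 0.7 | 0.850 | 85.7% | 2.60 | 0.55 |
| 1.0 | 0.8 | 0.900 | 83.7% | 2.67 | 0.45 |
| 1.0 | 0.9 | 0.950 | 81.7% | 2.74 | 0.32 |
| 0.8 | 0.3 | 0.784 | 88.3% | 2.49 | 0.66 |
| 0.8 | 0.5 | 0.893 | 84.0% | 2.66 | 0.46 |
| 0.8 | 0.7 | 0.981 | 80.5% | 2.79 | 0.20 |
| 0.8 | 0.8 | 1.000 | 79.7% | 2.82 | 0 |
| 0.8 | 0.9 | 0.950 | 81.7% | 2.74 | 0.32 (reversed) |
| 0.7 | 0.3 | 0.850 | 85.7% | 2.60 | 0.55 |
| 0.7 | 0.5 | 0.949 | 81.7% | 2.74 | 0.32 |
| 0.7 | 0.7 | 1.000 | 79.7% | 2.82 | 0 |
| 0.7 | 0.8 | 0.973 | 80.8% | 2.78 | 0.23 (reversed) |
| 0.7 | 0.9 | 0.826 | 86.7% | 2.56 | 0.59 (reversed) |

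The shift favours the arm that starts higher when ρ < k and the other arm when ρ > k (marked as reversed). At k = 1.0 it is 0.84/4.0 = 21% down to 0.32/4.0 = 8% of the target difference.

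Simulation with 20,000 trials per setting agreed: for example 89.9% adjusted at k = 1, ρ = 0.5, and 79.9% at k = ρ = 0.8, with the unadjusted test at 79.9% to 80.4% across the grid.

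**Step 5: the pilot recalculation.** A pooled change SD of 7.2 gives 52 per arm. Using the residual SD instead would give 40 per arm at a variance ratio of 0.75, or 35 at 0.65.

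**The case against.** **No error is being corrected.** The same endpoint, test and SD appear in sizing, analysis and recalculation, and the test has its stated power. This stands: the point is a missed improvement.

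**The benefit rests on unknown inputs.** The two ARI measurements are only 14 to 21 days apart, so a high correlation is plausible. At ρ of 0.7 to 0.8 with k of 0.7 or 0.8, power changes only from −0.4 to +0.7 points. The 93.4% figure needs a low correlation and equal SDs together. This also stands, and that figure should not be read as the expected result.

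**Some rows of the table may not be attainable.** Holding the change SD at 7.2 makes the implied baseline SD at k = 1 run from 6.1 (ρ = 0.3) to 16.1 (ρ = 0.9). The ARI has seven items, and the documents do not give the item scoring. If items ran from 0 to 2 (an assumption), the total would span 14 points and no SD could exceed about 7. The rows this removes are mostly those with little gain, so it does not reverse the direction. It does limit the table as evidence of size. The cap on the cost does not depend on the table.

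**Baseline is not wholly ignored.** Section 12.B mentions a covariate role for the callous-unemotional scale (ICU), and section 12.F plans a multivariate search for predictors of response. Neither is a treatment comparison of ARI adjusted for baseline ARI.

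**Conclusion.** The concern holds as a recommended improvement. The planned t-test is valid and correctly powered, but it leaves unused a baseline value that every child already provides. Because the variance ratio is 1 − r², the loss from adjusting is capped at about 0.4 percentage points of power at 52 per arm, whatever ρ and k are. The gain is uncertain: none when ρ = k, and up to 93.4% power in the most favourable row. The power figures assume the plan's difference of 4.0 and change SD of 7.2. The protection against a chance baseline difference also depends on ρ and k, and vanishes when ρ = k. A small, bounded cost against a possible material gain justifies the change, provided it is specified before unblinding, since adjustment chosen afterwards would be open to challenge.

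**What to change.** 1. **Section 12.F, test (1).** Make the primary analysis a linear model of final ARI on treatment with baseline ARI as covariate, at the two-sided 5% level. Report the adjusted mean difference with its 95% confidence interval. Modelling change instead of final ARI gives the same treatment estimate. Keep the unadjusted t-test as a sensitivity analysis.
2. **ARI version.** Section 12.B lists self-report and parent-report versions. State that the covariate and the outcome come from the same one.
3. **Secondary measures.** Use the matching baseline wherever one exists. No size of gain is claimed for these.
4. **Section 4.B and the internal pilot text in 12.F.** Keep 52 per arm and keep the pooled SD of change in the recalculation. Say that this is a deliberately conservative basis, since a residual SD from 20 children could cut the sample size sharply on an imprecise estimate.

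The cost is one degree of freedom and a short alignment of the text in sections 4.B and 12.F. No additional data or children are needed.

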##### **B. What is the age range for the child subjects, and what is the justification for selecting this age range?**

The age range for the child and adolescent subjects in this study is 10-18 years. The disorders included in this protocol have an onset of symptoms in childhood and adolescence

(American Psychiatric Association, 2013). The proposed age range in this protocol was also guided by our previous experience at National Institute of Mental Health conducting neuroimaging studies in youth with disruptive behavior disorders. In our experience, by age 10, 80-90% of participants can be successfully scanned and data are not often compromised by movement.

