**Neuroimaging:**

The clinical MRI scanning of brain will occur at the MRI visit 1, to rule out any anatomical abnormality of the participants brain, such as brain tumor, hemorrhage, or other structural abnormality. This will occur at the Boys Town National Research Hospital. During the MRI visit 1, participants will receive their first fMRI session immediately before initiation of oxytocin or placebo treatment. The fMRI visit 1 can happen on the same day of the initial research assessment after the initial research assessment is completed.

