**Withdrawal Criteria**

1. Initiation of any medication that may have psychotropic effects (newly introduced antidepressants, antipsychotics, anxiolytics, stimulants, and non-stimulant ADHD medications).

2. Discovery of neurologic disorder (including seizures) or anatomical abnormality of brain (including brain neoplasm, hydrocephalus) during participation.
3. Discovery of substance abuse or dependence.
4. Inability of the participant to complete fMRI or MEG due to claustrophobia despite previous questioning.
5. Participants who do not want to continue with the study.
6. Participants who cannot or will not cooperate with study procedures.
7. Participants who experience strong discomfort or develop side effect following the administration of oxytocin or placebo nasal spray.
8. Participants who experience significant worsening of psychiatric symptoms that warrant change of treatment (such as inpatient psychiatric hospitalization).

**G. Describe the specific criteria for halting or early termination of the study (for example statistical evidence of unacceptable toxicity or early demonstration of efficacy or lack of efficacy).**

The study would be halted in followings;

1. Early evidence showing lack of efficacy on irritability or worsening of irritability by oxytocin treatment: After the preliminary phase of the study (10 patients on each arms of oxytocin and placebo trial), if it turns out that children and adolescents experience significant worsening of their psychiatric/behavioral symptoms, or have no change in their psychiatric/behavioral symptoms, we then will consider terminating the study.
2. MEG and/or fMRI become inoperable
3. Serious injury related to procedure (MEG, fMRI, or oxytocin administration) occurs

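### The BOLD comparison is a change-score t-test on complete scan pairs: it should adjust for the baseline scan and state how missing scans are handled

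*Combined protocol and SAP*

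**What the plan says.** Item 12.F of the combined protocol and SAP tests Hypothesis A in three parts. Part (2), the neural comparison, is a two-sample t-test between placebo and "oxytocin-treated groups on the change of BOLD responses". Part (3) is an ANCOVA on the same BOLD change, with treatment group and symptom change as covariates; baseline BOLD is not among them. The documents define no analysis population, missing-data method or sensitivity analysis for BOLD.

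On timing, item 12.B says that "participants will receive their first fMRI session immediately before initiation of oxytocin or placebo treatment", and that "The second fMRI and MEG scans will be completed after 14-21 days of oxytocin/placebo treatment".

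On scan success, item 6.B gives the team's earlier experience in support of the lower age limit: "by age 10, 80-90% of participants can be successfully scanned and data are not often compromised by movement".

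The withdrawal criteria in item 18.F include "Inability of the participant to complete fMRI or MEG due to claustrophobia despite previous questioning", "Participants who experience strong discomfort or develop side effect following the administration of oxytocin or placebo nasal spray" and "Participants who experience significant worsening of psychiatric symptoms that warrant change of treatment".

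Items 4.A and 4.C set a target of 104 completers (52 per group) and at most 140 consented.

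**The concern.** A change score exists only when both scans are usable, so part (2) is a complete-pair analysis by construction. This has two consequences.

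- **Precision.** The change score fixes the coefficient of the baseline scan at 1 instead of estimating it. That is inefficient unless the two scans are very highly correlated. A child whose first scan failed and whose second is usable also contributes nothing.
- **Selection.** The first scan precedes treatment, so its failure costs data but does not by itself disturb the comparison. The second scan and the withdrawals for side effects or worsening come after randomisation. If the reasons for losing a second scan differ by arm and are related to BOLD, the children with complete pairs are no longer comparable between arms.

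A reduced amygdala response is half of Hypothesis A, and part (3) uses the same pairs.

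**Working it through.** **The plan's own figure.** Item 4.B plans for ARI change: difference 4.0, SD 7.2, two-sided 0.05, 80% power. The normal approximation gives n = 2 × (1.960 + 0.842)² × 7.2² / 4.0² = 50.9, so 51 per group. The exact t-test gives 79.3% power at 51 and 80.1% at 52, so the stated 52 reproduces. The documents give no power or sample size for BOLD.

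**Inputs for BOLD.** n = 52 per arm (item 4.A). Success per scan p = 0.8 or 0.9 is an assumption that reads the item 6.B figure as per scan. The pre-post correlation r = 0.2, 0.4, 0.6 is also assumed, as the documents give none. BOLD variance is set to 1 at both visits; formulas are large-sample, with loss unrelated to BOLD.

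**Variance of the treatment effect, failures independent across visits:**

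- Planned change-score t-test on pairs: 4(1−r)/(np²)
- Baseline-adjusted analysis of the same pairs: 2(1−r²)/(np²)
- Constrained longitudinal model (common baseline mean, all usable scans): 2/{n[p²/(1−r²) + p(1−p)]}

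In the third formula, p(1−p) is the share of children with a failed first and a usable second scan. Children with only a first scan do not appear: under a common baseline mean they carry no information on the difference between arms.

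At p = 0.8, r = 0.4:

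- Change score: 4 × 0.6 / (52 × 0.64) = 0.0721
- Baseline-adjusted pairs: 2 × 0.84 / (52 × 0.64) = 0.0505
- Constrained model: 2 / [52 × (0.64/0.84 + 0.16)] = 0.0417

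**Step 1: baseline adjustment alone.** The ratio of the second formula to the first is (1+r)/2. The number of pairs cancels, so the cut of (1−r)/2 does not depend on how many scans are missing.

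**Step 2: single scans in addition.** The further cut relative to adjusted pairs is 1 − 1/[1 + (1−p)(1−r²)/p].

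| r | Baseline adjustment alone | Further cut, p = 0.8 | Further cut, p = 0.9 |
|---|---|---|---|
| 0.2 | 40% | 19% | 10% |
| 0.4 | 30% | 17% | 9% |
| 0.6 | 20% | 14% | 7% |

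**Step 3: other loss patterns.** If only second scans are lost, adjusted pairs and the constrained model have the same variance, 2(1−r²)/(np). At p = 0.8, r = 0.4 that is 2 × 0.84 / (52 × 0.8) = 0.04038 for both. If the same children fail at both visits there are no single scans to use, and the further cut is again zero.

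**Step 4: bias.** A simulation used 52 per arm, no true effect on BOLD, nominal 5% and 4,000 runs per scenario. The scan-rescan correlation of 0.5 and the strength of dependence (probit slope 1) are assumptions.

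| Usability of the pair | Planned t-test, type I error | Baseline-adjusted, type I error |
|---|---|---|
| Random, 80% vs 90% usable | about 5% | about 5% |
| Depends on baseline BOLD in one arm only, 80% usable | about 9% | about 5% |
| Depends on BOLD change in one arm only, 90% usable | about 10% | about 9% |
| Depends on BOLD change in one arm only, 80% usable | about 21% | about 17% |

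Unequal loss alone does no harm. Baseline adjustment repairs selection on the observed baseline, but not selection on the unseen second value.

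**The case against.** The strongest case against is that the mixed model does little for the loss that matters. Randomisation is at risk through the second scan, and there the model gains nothing over baseline-adjusted pairs (step 3). All of its extra gain comes from children who fail the first scan and succeed at the second. The protocol makes such children less likely: spray starts only after the first MRI and MEG visits, and item 18.F withdraws children who cannot complete a scan because of claustrophobia or who do not cooperate. This stands. Motion-corrupted first scans may leave some such children, but the documents give no rate.

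Four stronger readings are tempting and are not supported:

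- **That the plan expects 10-20% scan failure.** Item 6.B reports earlier experience by age 10, for a trial of ages 10-18. It does not say whether the figure is per scan or per child, and it adds that movement seldom spoils the data.
- **That only 67-84 of the 104 would have both scans.** This multiplies 104 by 0.64-0.81, but 104 is a completer target. With 140 consented, total loss can reach 1 − 104/140 = 25.7%, so some lost children may be replaced. The 140 must also cover screen failures, however (104/0.8 = 130; 104/0.64 = 163), and replacement does not restore comparability.
- **That missing scans explain the whole gain over the planned test.** With independent failures the combined cut is 31-52% (80% success) or 25-46% (90%), but 20-40 percentage points of that are plain baseline adjustment and would arise with no scan missing.
- **That the comparison is already biased towards calmer children.** Nothing in the documents shows that the children lost are the more irritable ones, or that loss differs by arm. Nor is their ARI discarded: a child with a failed scan who completes the final assessment still counts in part (1).

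It is also fair to say that the form asks only for a brief description of methods, and that ARI change is the primary outcome.

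**Conclusion.** The point holds as a matter of efficiency and of an unstated missing-scan rule. It does not show that the neural result would be biased. Part (2) uses complete pairs only and leaves the baseline scan out as a covariate. Adjusting for it cuts the variance of the treatment effect by 20-40% over assumed correlations of 0.6 down to 0.2, given equal variances at the two visits. The further gain from single scans, 7-19%, rests on failures being independent across visits and may be zero here.

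Treatment-related loss at the second visit is a possibility that the plan neither measures nor addresses. The proposed model reduces the resulting bias when loss depends on observed baseline BOLD or ARI, and not when it depends on the second scan itself. The primary ARI analysis and the stated 52 per group are unaffected by this point. The change is worth making, at secondary priority.

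**What to change.** In item 12.F, replace part (2) with a baseline-adjusted comparison of second-visit amygdala BOLD, fitted as a constrained longitudinal model:

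- Terms for visit and arm-by-visit, a baseline mean common to both arms, and unstructured covariance.
- Every randomised child with at least one usable scan included, with baseline ARI as a covariate.
- Usable-scan rates reported by arm and visit.
- The complete-pair t-test kept as a sensitivity analysis.
- A missing-not-at-random sensitivity analysis, in which missing second-visit values are shifted by arm over a stated range.

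The cost is SAP wording and a standard mixed model; no new data or visits are needed. The main model relies on scans being missing at random given the baseline scan and ARI. That is weaker than what the complete-pair t-test needs, but the data cannot confirm it, which is why the last item belongs in the plan.
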